We will conduct a similar analysis for secondary and tertiary outcomes, including key secondary outcomes such as the PEG and will use appropriate link functions for non-continuous outcomes. All models will adjust for baseline outcome value, age, sex, and HCS as well as any baseline variables that are predictive of loss to follow-up. All analyses will be conducted following an intent-to-treat approach, including all individuals randomized regardless of their engagement with, or exposure, to the intervention. If loss to follow-up is above 15%, we will employ imputation techniques to address missing data issues.¹⁰⁴ However, our focus will be on minimizing loss to follow-up and in our collective substantial experience conducting similar trials, we have consistently had retention in line with this. The imputation method that we were referencing uses a pattern mixture approach that relaxes the missing at random assumption. This approach that we propose using is derived for GEE and is sensitive to potential non-ignorable missingness.¹⁰⁴

Exploratory analyses will further use tertiary outcome data collected monthly (i.e., the PEG and PROMIS®, Physical Function). We will use these measures to assess the trajectory of how long it takes until patients improve and to address questions such as “What proportion of people improve at three months if they don’t improve after one or two months of acupuncture?” These exploratory analyses will help address how much acupuncture is needed to improve and at what time, given a patient’s outcome trajectory, should acupuncture treatment stop if improvement has not been shown up to that time.

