## 9. Missing Data

The investigators and data managers will monitor data collection process on a weekly basis and ensure a minimal amount of loss to follow-up in the study. All analyses will be conducted following an intent-to-treat approach, including all individuals randomized regardless of their engagement with, or exposure, to the intervention. If missing data for RMDQ is minimal, our primary analysis will be a complete case analysis adjusting for baseline RMDQ score, age, sex, race and HCS. If missing data for RMDQ at 6 months is above 15% in any arm, or differential by 10% between any two arms, then for our primary analysis we will employ missing not at random imputation techniques to address missing data issues. Though the metric used to make decisions about the analysis method focuses on missing data at the primary time point (6 months), if criteria are met missing data will be imputed 3, 6 and 12-month time points. However, our focus will be on minimizing missing data, and in our collective substantial experience conducting similar trials, we have consistently had retention in line with this. Should it be necessary, the imputation method we propose, derived for use with GEE and sensitive to potential non-ignorable missingness, includes all follow up time points in the same model and uses a pattern mixture approach that relaxes the missing at random given baseline covariates assumption. This accomplished via the implementation of an imputation model which includes indicators classifying the mutually exclusive missing data patterns observed across all time points in the data. We will describe all of the missing data patterns present in the observed data to identify a scientifically reasonable and estimable set of patterns to use as indicators in imputation models for each outcome. Specifically, following the recommendations of Wang and Fitzmaurice, we plan to use the most flexible (parameterizing the largest number of missing patterns) that are estimable with the data. We will construct the imputation models such that the effects of missing data on the outcome are allowed to vary by treatment arm and follow-up time and will include main effects for all covariates used as stratification factors in the study randomization and/or thought to be potential confounders of the relationship between outcome and treatment arm. Further, we will include additional baseline variables that are predictive of missing the 6 months outcome. Specifically, baseline covariates that are significantly (at 0.10 significance level) associated with missingness at 6 months using flexible logistic regression models will be included as main effects in imputation models.

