## 13. Effectiveness Analyses on Changes in RMDQ Scores

We will evaluate the effectiveness of acupuncture and acupuncture plus maintenance relative to Usual Medical Care (UMC) at 3-, 6- (primary time-point), and 12-months after randomization. We will conduct a longitudinal analysis including the continuous outcome, change in Roland Morris Disability Questionnaire (RMDQ) from baseline (primary outcome) measured at all follow-up times, in one model estimated using generalized estimating equations (GEE).  We will use a working independence correlation matrix and will calculate standard errors using the robust sandwich estimator to account for within-person and within-in provider (some participants may see the same provider) correlation. All models will adjust for baseline RMDQ score, age, sex, race and HCS. Further, if missing RMDQ at 6 months (primary time point) is more than 15% in any study arm, or differential by more than 10% between any two arms, we will use imputation approaches as the primary analysis to account for missing data and further adjust for any baseline variables that are predictive of loss to follow-up determined as described in Section 9. All analyses will be conducted following an intent-to-treat approach, including all individuals randomized regardless of their engagement with, or exposure, to the intervention.

We will include interactions between intervention groups and time (3-, 6-, and 12-months) to estimate time-specific intervention effects. Time will be included as a categorical variable. To gain power, since acupuncture and acupuncture plus maintenance at 3-months are the same intervention (maintenance period occurs between 3 and 6 months post randomization and neither participants in the EA condition nor the acupuncturists treating them will be aware they will receive maintenance treatments until close to the 3-month follow-up), we will combine acupuncture groups at 3-month follow-up. We chose GEE as our analytic method because our primary outcome, RMDQ, is not expected to be normally distributed. From our experience working with RMDQ data, adjusting for baseline RMDQ value results in more normally distributed residuals. However, we didn't want to make that assumption a priori and therefore chose GEE.

Our specific model for change in RMDQ is the following:

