### 13.2 Secondary Time Points: 3- and 12-Months Post Randomization

The acupuncture's impact on the change of RMDQ scores at 3-months will be assessed by testing if  $\beta_{Acu} = 0$  in equation (1) since acupuncture and acupuncture plus maintenance at 3-months are the same intervention (maintenance period occurs between 3 and 6 months post randomization and neither participants in the EA condition nor the acupuncturists treating them will be aware they will receive maintenance treatments until close to the 3-month follow-up). We will follow the same general framework for 12-months as we have specified for 6-months in Section 13.1. Note that the analysis focused on the 12-month follow-up timepoint provides an important test of whether EA makes an appreciable difference over SA in sustaining or improving the effect of acupuncture on pain-related functioning that endures after the end of treatment. Finally, note that we include all times points in a single GEE model within this general modeling framework to handle correlation due to multiple outcomes on a given person. We will report both the fully saturated model 1 results and an additional final model if scenario 2 is correct for either 6 or 12 months. For example, if scenario 2 is concluded for both time points 6 and 12 months the final model is:

Scenario 2 is correct for 6 and 12 months:

$$(2) \quad E(Y_{im}|T_i, Z_i) = \alpha + \beta_{Acu}I(T_i = SA \text{ or } EA) + \beta_z Z_i + \beta_6 I(m = 6) + \beta_{12} I(m = 12) \\ + \gamma_{Acu,6} I(T_i = SA \text{ or } EA)I(m = 6) + \gamma_{Acu,12} I(T_i = SA \text{ or } EA)I(m = 12).$$

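### If 6-month RMDQ missingness stays within limits but 12-month missingness does not, the SAP prespecifies no imputation or sensitivity analysis for the 12-month EA-versus-SA test

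*SAP*

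**What the plan says.** SAP section 9 starts from a default: "If missing data for RMDQ is minimal, our primary analysis will be a complete case analysis". It gives no figure for minimal and names no visit. The switch to imputation is then defined: "If missing data for RMDQ at 6 months is above 15% in any arm, or differential by 10% between any two arms". SAP section 13 repeats it: "if missing RMDQ at 6 months (primary time point) is more than 15% in any study arm". Section 9 acknowledges that one visit decides for all, "Though the metric used to make decisions about the analysis method focuses on missing data at the primary time point (6 months", and says that "if criteria are met missing data will be imputed 3, 6 and 12-month time points". The baseline variables added to the imputation model are also chosen at one visit: "baseline covariates that are significantly (at 0.10 significance level) associated with missingness at 6 months".

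Protocol 9.6 has a simpler rule: "If loss to follow-up is above 15%, we will employ imputation techniques to address missing data issues". It names no visit and has no per-arm or between-arm limit.

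On the role of 12 months, SAP 13.2 states that "the analysis focused on the 12-month follow-up timepoint provides an important test of whether EA makes an appreciable difference over SA". The outcome tables in SAP section 2 label baseline to 12 months as the test of the maintenance effect.

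**The concern.** The rule covers one direction only. High missingness at 6 months brings in imputation at 12 months, but high missingness at 12 months brings in nothing. Loss to follow-up usually accumulates, so 12 months is the visit most likely to pass a 15% limit, and it carries the longer-term test of maintenance.

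The sensitivity analyses in SAP section 9 do not fill the gap. They vary the imputation model (pattern effects by site, choice of patterns), so they presuppose that imputation has been triggered.

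A silent trigger is also what the team hopes for. SAP section 9 reports that retention in similar trials has been in line with its aim of little missing data, and Protocol 10.3.3 aims for at least 85% follow-up at each monthly survey. At stake is a named secondary comparison, which could be reported without any analysis that allows dropout to depend on outcome.

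**Working it through.** **1. The plan's own loss figure.** SAP section 4 expects 630 of 789 participants (210 of 263 per arm) to complete 6 months. Check: 210 / 0.80 = 262.5, rounded up to 263. The planned 6-month missingness is (789 − 630) / 789 = 20.2%. The power figures also reproduce. With 210 per arm, SD 6, a 2-point difference and Fisher's LSD, simulated pairwise power is about 0.91, against the stated 90% and 91%.

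**2. When the 6-month trigger fires.** 15% of 263 is 39.45, so an arm passes the limit at 40 or more missing. With the same true missing rate in all three arms and binomial counts, the chance that the trigger fires is:

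| True 6-month missingness | P(trigger) |
|---|---|
| 10% | 0.015 |
| 12% | 0.19 |
| 14% | about 0.67 |
| 15% | 0.87 |
| 20% | 1.00 |

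At the planned loss, 12 months is imputed and the gap does not arise. It opens when 6-month missingness is about 14% or lower and rises later.

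**3. How often 6 months is silent while 12 months passes the same limits.** The documents give no 12-month rates, so these pairs are assumptions (263 per arm, cumulative loss, equal rates by arm):

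| 6 months | 12 months | P(6 months silent, 12 months over) |
|---|---|---|
| 8% | 16% | 0.96 |
| 10% | 18% | 0.98 |
| 12% | 18% | 0.81 |
| 14% | 18% | 0.33 |

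**4. Whether the joint model recovers 12-month dropouts.** It does not. SAP section 13 uses working independence. In model (1) each arm has its own 12-month mean (the intercept plus the 12-month term for UMC, with the SA and EA terms added), so only the covariate slopes are shared with other visits. Section 9 itself says that standard GEE assumes data missing at random given baseline covariates. A simulation agrees. It assumed about 10% missing at 6 months, 17% to 19% at 12 months, a true EA−SA difference of 0 and strong outcome-dependent dropout in EA. Over 1,500 trials the mean 12-month EA−SA estimate was −1.135 from the joint model and −1.140 from a 12-month-only complete-case fit (correlation 0.999). This shows that the two analyses are in effect the same; its size is not a forecast.

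**5. Size of possible bias.** The unadjusted bias in EA−SA is m(EA) × d(EA) − m(SA) × d(SA), where m is the missing share and d the completer-minus-dropout difference in mean score. Assumed examples:
- 18% missing in both arms, d = 2 in both: 0.18 × 2 − 0.18 × 2 = 0.
- 20% and 15% missing, d = 3 and 1: 0.20 × 3 − 0.15 × 1 = 0.45 point.
- 24% and 14% missing, d = 4 and 0: 0.24 × 4 − 0.14 × 0 = 0.96 point.

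The sign reverses if the arms are swapped. For scale, SAP 13.1 counts an EA−SA difference as meaningful when it exceeds 1 point.

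A second calculation uses SD 6 (SAP section 4), a true effect of 2.0, 22% missing per arm at 12 months, between-visit correlation 0.65 and dropout driven by 3-month RMDQ. Only the SD and the 2.0 come from the plan. Complete-case estimates, adjusted for baseline:

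| Dropout odds per SD of score | Estimate |
|---|---|
| 2, same direction in both arms | 2.0 |
| 2, one arm only | 1.81 |
| 1.25, opposite directions | 1.86 |
| 1.5, opposite directions | 1.76 |
| 2, opposite directions | 1.6 |
| 2, opposite directions, arms swapped | 2.4 |

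**The case against.** The best defence is that the SAP chose a single decision rule, at the primary visit, for a single joint model, and extended imputation to all visits once the rule is met. Under the planned loss that covers 12 months. This stands, and it makes the point conditional.

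Several stronger readings are tempting, but the documents do not support them:

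- *The 12-month test is always complete-case.* It is not: a met trigger imputes 12 months too. Even a true 14% at 6 months fires the trigger in about two trials of three.
- *The plan itself calls more than 15% missing at 12 months unacceptable.* The SAP's 15% is a switch of method defined at 6 months, and the same plan budgets for 20% loss. Only the Protocol's undated rule carries 15% to other visits.
- *The SAP contradicts the Protocol.* It is narrower on timing but stricter by arm. The texts need aligning, and that is all.
- *The effect is pulled towards zero by about a fifth.* The 1.6 is one end of a range that includes no bias and bias the other way. The true effect of 2.0 is the planning difference against UMC, whereas EA versus SA is not expected to reach clinical importance. What carries over is the shift of up to about 0.4 point.
- *The cost-effectiveness ratio inherits the problem.* SAP section 18 states no missing-data method and does not say whether imputed RMDQ would be used, so a change to sections 9 and 13 would not settle it.

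It is also fair to object that switching method visit by visit sits badly with one joint model. A separate 12-month analysis avoids that.

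**Conclusion.** The gap is real and limited. It exists only when 6-month missingness is within limits and 12-month missingness is not. In that case SAP sections 9 and 13 name no imputation or sensitivity analysis for the 12-month EA-versus-SA comparison, and the independence GEE does not use earlier scores to make up for 12-month dropouts. At the planned 20% loss it almost certainly does not arise. With better 6-month retention (8% to 12%) and 16% to 18% missing at 12 months, it would arise in roughly 80% to 98% of trials.

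The bias is zero if dropout works alike in the two arms and about 0.4 point in either direction under the opposed-dropout illustration. All of this rests on assumed 12-month rates, correlation and dropout mechanisms. Neither the 6-month primary analysis nor the 6-month test of EA against SA is touched. The change is worth making because 12 months is a named secondary test and the remedy is cheap.

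**What to change.** In SAP sections 9 and 13, add that if 12-month RMDQ missingness exceeds 15% in any arm, or differs by more than 10% between any two arms, the pattern-mixture imputation analysis is also run for 12 months. Its model should include baseline predictors of 12-month as well as 6-month missingness. The result should be reported beside the complete-case 12-month result. State plainly that this does not change the method for the 6-month primary analysis.

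Align the trigger wording with Protocol 9.6 so that both documents name the visits and the per-arm and between-arm limits.

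The cost is a few sentences. The planned imputation model already covers all follow-up visits, so the extra analysis is small. The downside is two 12-month estimates to report and explain.

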## 10. Outlier Measures

The occurrence of outlier measures in this study will be unlikely since most measurements are obtained from questionnaires with a limited range of values; range and logic checks will be built into the outcomes database. Thus, we will not correct for any outlier in the effectiveness analyses.

## 11. Demographic and Baseline Characteristics

Demographic variables, including sex, age, race and ethnicity, will be extracted from EHR, and summarized for each intervention arm. We define baseline characteristics as information collected during baseline interview (pre-randomization), including but not limited to employment status, education, marital status, income, tobacco use, alcohol use, duration of pain condition or any variables potentially associated with primary and secondary outcomes, moderating the impact of acupuncture treatments, and predictive for loss to follow-up.

## 12. Descriptive Analysis

Descriptive statistics for all follow-up data will be provided for each intervention. For continuous variables we will include the mean, median, SD, maximum and minimum. Frequencies, percentage, and tabulations will be provided for categorical variables. Summary statistics will be performed on patient demographics and baseline characteristics.

## 13. Effectiveness Analyses on Changes in RMDQ Scores

We will evaluate the effectiveness of acupuncture and acupuncture plus maintenance relative to Usual Medical Care (UMC) at 3-, 6- (primary time-point), and 12-months after randomization. We will conduct a longitudinal analysis including the continuous outcome, change in Roland Morris Disability Questionnaire (RMDQ) from baseline (primary outcome) measured at all follow-up times, in one model estimated using generalized estimating equations (GEE).  We will use a working independence correlation matrix and will calculate standard errors using the robust sandwich estimator to account for within-person and within-in provider (some participants may see the same provider) correlation. All models will adjust for baseline RMDQ score, age, sex, race and HCS. Further, if missing RMDQ at 6 months (primary time point) is more than 15% in any study arm, or differential by more than 10% between any two arms, we will use imputation approaches as the primary analysis to account for missing data and further adjust for any baseline variables that are predictive of loss to follow-up determined as described in Section 9. All analyses will be conducted following an intent-to-treat approach, including all individuals randomized regardless of their engagement with, or exposure, to the intervention.

We will include interactions between intervention groups and time (3-, 6-, and 12-months) to estimate time-specific intervention effects. Time will be included as a categorical variable. To gain power, since acupuncture and acupuncture plus maintenance at 3-months are the same intervention (maintenance period occurs between 3 and 6 months post randomization and neither participants in the EA condition nor the acupuncturists treating them will be aware they will receive maintenance treatments until close to the 3-month follow-up), we will combine acupuncture groups at 3-month follow-up. We chose GEE as our analytic method because our primary outcome, RMDQ, is not expected to be normally distributed. From our experience working with RMDQ data, adjusting for baseline RMDQ value results in more normally distributed residuals. However, we didn't want to make that assumption a priori and therefore chose GEE.

Our specific model for change in RMDQ is the following:

$$(1) \quad E(Y_{im}|T_i, \mathbf{Z}_i) = \alpha + \beta_{Acu}I(T_i = SA \text{ or } EA) + \boldsymbol{\beta}_z \mathbf{Z}_i + \beta_6 I(m = 6) + \beta_{12} I(m = 12) \\ + \gamma_{SA,6} I(T_i = SA) I(m = 6) + \gamma_{SA,12} I(T_i = SA) I(m = 12) \\ + \gamma_{EA,6} I(T_i = EA) I(m = 6) + \gamma_{EA,12} I(T_i = EA) I(m = 12)$$

where  $Y_{ij}$  is the change in RMDQ score from baseline for individual  $i$  at time point  $m$ ,  $T_i$  is the intervention group,  $m$  is the number of months post randomization, and  $Z_i$  is the vector of baseline covariates as stated in the beginning of this section, respectively. The parameters  $\alpha$ ,  $\beta$ 's and  $\gamma$ 's are the intercept, main effects, and the interaction effects of the corresponding category indicators in the subscripts.

### 13.1 Primary Time Point: 6-Months Post Randomization

For the 6-month time point we will conduct a sequential series of analyses after fitting the model in equation (1). The difference in change in RMDQ at 6-months between the two acupuncture groups, SA and EA, will be assessed first by testing  $\gamma_{SA,6} = \gamma_{EA,6}$ . If a statistically significant ( $\alpha=0.05$ ) and meaningful difference ( $>1$  pt difference) is found between SA and EA (Scenario 1), comparisons of each acupuncture group to UMC will be carried out individually. Scenario 1 assessments will determine (1) if acupuncture treatment with additional maintenance period (EA) is better than the standard acupuncture treatment (SA) at 6-months and (2) if either or both acupuncture groups are better than UMC. In an alternative scenario where SA and EA do not differ at 6-months (Scenario 2), the two acupuncture groups will be combined for the time point of 6-months and run a second regression model (Model 2) including only UMC and the combined acupuncture group. If this regression model shows that acupuncture is better than UMC, we will conclude that acupuncture improved RMDQ at 6-months, but maintenance was not shown to be effective.

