For the 6-month time point we will conduct a sequential series of analyses. We will first run a regression model with three groups (acupuncture [SA], acupuncture plus maintenance [EA] and UMC) for the 6-month follow-up. We will then assess differences in change in RMDQ at 6-months between the two acupuncture groups: with (EA) and without (SA) maintenance. If a statistically significant ($\alpha=0.05$) and meaningful difference (>1 point difference) is found between the maintenance (EA) versus no maintenance (SA) groups (Scenario 1), we will further compare each of the acupuncture groups separately to UMC. Scenario 1 assessments will determine if acupuncture with maintenance (EA) is better than acupuncture without maintenance (SA) at 6-months and if either or both acupuncture groups are better than UMC. If acupuncture groups do not differ at 6-months (Scenario 2), we will combine acupuncture groups for this time point and run a second regression model including only UMC and the combined acupuncture group. If this regression model shows that acupuncture is better than UMC, we will conclude that acupuncture improved RMDQ at 6-months, but maintenance was not shown to be efficacious.

We will follow the same general framework for 12-month as we have specified for 6-months. Note that the analysis focused on the 12-month follow-up timepoint provides an important test of whether maintenance (EA) makes an appreciable difference over standard acupuncture in sustaining or improving the effect of acupuncture on pain-related functioning that endures after the end of treatment. Finally, note that we include all time points in a single model within this general modeling framework to handle correlation due to multiple outcomes on a given person.

To control for multiple comparisons when testing between the three groups at 6-months we will use Fisher's least significant (LSD) difference procedure.¹⁰² Fisher's LSD has been shown to strongly hold the family-wise error rate at α -level for studies with three treatment groups.¹⁰³ Fisher's LSD is a simple procedure where the global Wald-test of the null hypothesis of equal means for all groups is performed first. If this overall test is statistically significant then the sequential series of pairwise comparisons will be performed as outlined previously; otherwise the procedure stops, failing to reject the over null hypothesis that at least one mean is different

from the others.

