## **8. Multiple Comparisons**

We have one primary outcome – the change on RMDQ scores for low-back pain related disability at 6 months since baseline. To control for multiple comparisons due to 3 intervention groups we will apply Fisher's Least Significant Difference approach in which first an omnibus Wald-test for any statistically significant difference

between the three groups is evaluated at the 0.05 alpha level. If the omnibus test is statistically significant, then the pair-wise differences are then evaluated, each using two-sided alpha=0.05. If the omnibus test is not statistically significant, we will conclude that there is no benefit of acupuncture for that time point. In addition, secondary analyses will use a similar approach as that described for the primary outcome to control for the three group comparisons.

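### The primary 6-month conclusion follows an EA-versus-SA-first pooling rule, but the pairwise power stated in SAP 4 and protocol 9.2 belongs to plain Fisher LSD, the rule in SAP 8

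*SAP*

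**What the plan says.** SAP 8 gives the rule for the single primary outcome, change in RMDQ at 6 months: an omnibus Wald test at 0.05, and then "If the omnibus test is statistically significant, then the pair-wise differences are then evaluated, each using two-sided alpha=0.05". That is ordinary Fisher LSD for three arms. If the omnibus test fails, the conclusion for that time point is no benefit.

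SAP 13.1 gives a decision tree for the same outcome. EA is compared with SA first. If the difference is significant at 0.05 and exceeds 1 point (Scenario 1), each arm is compared with UMC. If not (Scenario 2), "the two acupuncture groups will be combined for the time point of 6-months and run a second regression model (Model 2". When that model favours acupuncture, "we will conclude that acupuncture improved RMDQ at 6-months, but maintenance was not shown to be effective". SAP 13.1 neither mentions the omnibus test nor refers to SAP 8.

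Protocol 9.6 has the same tree ("we will combine acupuncture groups for this time point and run a second regression model including only UMC and the combined acupuncture group") but places the omnibus test in front of it: "If this overall test is statistically significant then the sequential series of pairwise comparisons will be performed as outlined previously". It justifies this by stating that Fisher's "LSD has been shown to strongly hold the family-wise error rate at" the alpha level with three treatment groups.

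SAP 4 and protocol 9.2 state power per pairwise comparison: at least 90% for 2 points between each acupuncture arm and UMC, and 91% for EA versus SA and EA versus UMC if SA has faded to the UMC level. SAP 4 says the simulation used Fisher LSD. The primary hypothesis (SAP 1.1, protocol 1.1) is that each of the two courses beats UMC. It adds that EA will be superior to SA, but not by a clinically important amount. SAP 13.2 says the full model (1) is reported beside the pooled model whenever pooling occurs.

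**The concern.** One primary endpoint has two decision rules, and they differ on when an arm is tested against UMC. The stated power belongs to the LSD rule, whereas the conclusion is drawn by the tree. Because the plan expects EA and SA to lie close together, pooling is the path it should expect to take. The arm-versus-UMC comparisons on which the trial was sized would then usually not be the confirmatory ones.

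At stake is what the trial can say about each course. A pooled result supports a statement about the average of SA and EA against UMC. The primary hypothesis concerns each arm. The distinction is easy to lose, because elsewhere the documents use the word acupuncture alone for the SA arm. Protocol 9.6 describes a "regression model with three groups (acupuncture [SA], acupuncture plus maintenance [EA] and UMC) for the 6-month follow-up", and SAP 13 begins "We will evaluate the effectiveness of acupuncture and acupuncture plus maintenance relative to Usual Medical Care (UMC".

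**Working it through.** **Inputs.** 210 analysed per arm, SD 6, a 2-point difference, omnibus alpha 0.05, pairwise two-sided alpha 0.05 (SAP 4, SAP 8); tree thresholds p<0.05 and more than 1 point (SAP 13.1, protocol 9.6); change-score SD 5.11 as a sensitivity value (SAP 4). Effects below are points of benefit over UMC.

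**The plan's own figures.**
- Pairwise SE = 6 × √(2/210) = 0.586. The 95% half-width is 1.96 × 0.586 = 1.15, as stated in SAP 4.
- One ungated test of 2 points: 2/0.586 = 3.416, and Φ(3.416 − 1.96) = 0.927.
- With the omnibus gate (LSD, simulated): 91% for each arm versus UMC when both gain 2 points, and 91% for EA versus SA and EA versus UMC when only EA does. The stated power reproduces, as the power of LSD.

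**The tree.** Arm means were simulated as independent normals, with the omnibus test as a 2-df chi-square gate. The separate branch is taken if EA versus SA is significant and differs by more than 1 point. Otherwise the pooled contrast is tested, with SE = 6 × √(1/420 + 1/210) = 0.507. At SD 6 significance already needs 1.15 points, so the 1-point condition adds nothing. At SD 5.11 significance needs 0.98, so it binds slightly.

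| True benefit, SD 6 | Separate tests run | Separate EA-UMC claim, tree | EA-UMC claim, LSD | Some benefit shown, tree | Some benefit shown, LSD |
|---|---|---|---|---|---|
| SA=2, EA=2 | 5.0% | 4.1% | 91% | 95.1% | 95.1% |
| SA=0, EA=2 | 91% | 87% | 91% | 90.7% | 91.2% |
| SA=1, EA=2 | 39% | 39% | 87% | 86.2% | 87.1% |

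In the first row the pooled conclusion is reached in 90% of trials. In the second row EA-versus-SA power stays at 91%. The third row is not a scenario for which the plan states power. With SA=2 and EA larger by 0.5, 1 or 1.5 points, separate tests are run in 14%, 40% and 73% of trials.

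At SD 5.11 separate tests are run in 4.5% of trials when both arms gain 2 points. With SA=0 and EA=2, separate EA-UMC power is 96% (LSD 98%).

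**Error.**
- Global null, with the gate: any significant conclusion in 4.7% of trials.
- Separate branch: every rejection there has passed the omnibus test and a 0.05 pairwise test, so it is also an LSD rejection. Pairwise error cannot exceed that of LSD. With SA=0 and EA=1, 1.25 or 1.5, false favourable SA claims from this branch occur in 0.1%, 0.3% and 0.7% of trials.
- Pooled branch, read as the average: if the average equals UMC although the arms differ (SA=−0.5, EA=+0.5), pooled claims occur in 2.0%.
- Pooled branch, read as a claim for SA: with SA=0 and EA=1, 1.25 or 1.5, a false favourable SA claim occurs in 7.6%, 8.6% and 8.2% of trials in total, against 2.1% to 2.4% under LSD.

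**The case against.** The tree is prespecified and identical in the two documents, and it costs at most about one point of power to show some benefit. SAP 8 applies the omnibus gate to the 6-month primary outcome, so its absence from SAP 13.1 is a missing cross-reference. Model (1) is always reported, so both arm-versus-UMC estimates will be seen. The shortfall in the plan's second scenario is 87% against 91%. At SD 5.11 it is 96%, above the target, although SAP 4 chose 6 as an allowance for clustering and variability. If EA exceeds SA by 1.5 points, separate tests are run in most trials. All of this stands.

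Three stronger readings are tempting, and the documents do not support them.
- A reader might infer that family-wise control fails outright. It does not: the separate branch rejects only where LSD would, and a positive pooled test when only EA works is a true statement about the average. The figure of about 8% needs the pooled result to be turned into a claim about SA. SAP 13.1 uses the labels SA and EA and defines the combined group just before its conclusion, so that reading is possible but is not what the section says.
- A reader might infer that nothing says what is concluded when the pooled test is positive and the model (1) SA-versus-UMC contrast is not. SAP 13.1 states the conclusion drawn from the pooled model, and SAP 13.2 calls it the final model.
- A reader of SAP 13.1 alone might infer an ungated tree, with a global-null error of 9.8%. SAP 8 and protocol 9.6 both supply the gate.

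**Conclusion.** The point holds in a limited form. SAP 8 and SAP 13.1 give different rules for the primary endpoint, and the pairwise power in SAP 4 and protocol 9.2 is not the power of the rule that draws the conclusion. With both arms 2 points better, the separate tests are run in about 5% of trials. If only EA works, separate EA-versus-UMC power is 87%, not 91%. Power to show some benefit is kept (95% and 91%), and global-null and pairwise errors are controlled with the gate. What is lost when the arms are similar is a confirmatory answer for each course. Error rises, to about 8% against about 2.3% under LSD, only under an SA-specific reading of the pooled result.

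The figures assume independent normal outcomes with no provider clustering, covariate adjustment or imputation. The mismatch between the rules does not depend on them.

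**What to change.** Reconcile SAP 8, SAP 13.1 and protocol 9.6 on one confirmatory procedure before database lock, and cross-refer SAP 13.1 to the omnibus gate in SAP 8. The sponsor can choose between two routes.

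(i) After a significant omnibus test, make EA versus UMC, SA versus UMC and EA versus SA from model (1) the confirmatory contrasts, each at two-sided 0.05. Report the pooled estimate as supportive, described as the average of the two arms. This matches the stated power and the cited error property. The cost is a change of confirmatory procedure, not only of wording, and the narrower pooled interval becomes supportive. The chance of at least one positive arm-versus-UMC result is not reduced in the scenarios tabulated. With both arms at 2 points, 91% per arm becomes 87% for both together; the plan promises no joint figure.

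(ii) Keep the tree. Restate power for it, limit the Scenario 2 conclusion to the average of SA and EA versus UMC, and say that the LSD family-wise property does not extend to an SA-specific or EA-specific reading of the pooled result. The cost is that some stated power figures become less favourable.

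Neither route changes the data collected or the sample size.
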